**LENGTH OF STUDY**

The total duration of the study for each patient will be up to 40 weeks, divided as follows:

- Screening: up to 4 weeks
- Baseline: Day 1
- Study Treatment Administration: from Day 1 to Week 32
- Final safety and efficacy period: from Week 32 to Week 36

**END OF STUDY**

The end of the study is defined as the date when the last patient last observation (LPLO) occurs. LPLO is expected to occur 36 weeks after the last patient is enrolled.

---

## **OUTCOME MEASURES**

### **SAFETY OUTCOME MEASURES**

#### ***Adverse events***

Adverse events and concomitant medications will be monitored throughout the entire study.

#### ***Vital signs***

Body temperature (oral or tympanic) will be collected at the time-points indicated in the schedule of assessments (SoA).

BP and pulse rate will be performed after the patient has rested for at least 5 minutes at the time-points indicated in the SoA.

#### ***Electrocardiograms***

12-lead triplicate electrocardiogram (ECG) will be performed at the time-points indicated in the SoA.

#### ***Ocular safety***

Visual acuity will be assessed using best correction determined from protocol refraction (BCVA) using ETDRS-like charts, slit lamp examination, dilated binocular indirect high-magnification ophthalmoscopy, IOP, fundus photography, SD-OCT, and angiography will be performed at the time-points indicated in the SoA.

#### ***Laboratory tests***

Hematology, blood chemistry, and urinalysis, listed below, will be collected at the time-points indicated in the SoA.

- Hematology: Hemoglobin, hematocrit (HCT), red blood cell count, mean corpuscular volume (MCV), mean corpuscular hemoglobin (MCH), platelet count, total and differential white blood cell count (neutrophils, lymphocytes, monocytes, eosinophils, and basophils in absolute numbers), erythrocyte sedimentation rate (ESR)
- Coagulation (at screening only): Activated partial thromboplastin time (APTT) and prothrombin time/International Normalized Ratio (PT/INR)
- Blood chemistry: Sodium, potassium, bicarbonate, phosphate, chloride, calcium, urea, creatinine, total bilirubin, alkaline phosphatase (ALP), aspartate aminotransferase (AST), alanine aminotransferase (ALT), creatine phosphokinase (CPK), gamma glutamyl transferase (GGT), total protein, glucose, HbA1C (at screening and at final or early termination visits only), total cholesterol (TC), triglycerides (TG), C-reactive protein (CRP)
- Urinalysis: A midstream, clean-catch urine specimen will be collected for dipstick analysis of protein, blood, glucose, and pH. Microscopy to be performed if abnormalities are observed and deemed necessary by the Investigator or Designee, in particular when blood or protein is positive or strong positive
- Pregnancy test: for females of childbearing potential, serum pregnancy test at screening

#### ***Anti-drug antibodies***

Plasma samples will be collected at the time-points indicated in the SoA to evaluate the presence of anti-RO6867461 antibodies.

### **PHARMACOKINETIC OUTCOME MEASURES**

#### ***Plasma levels of RO6867461***

Plasma concentrations will be measured by a specific enzyme-linked immunosorbent assay (ELISA) method. The pharmacokinetic (PK) analysis is described in the statistical methods section. Samples may also be analyzed for ranibizumab.

#### ***Aqueous humor samples (optional)***

Samples will be collected from patients who provide additional (optional) consent to participate in aqueous humor collection. Samples will be analyzed for RO6867461 and biomarker concentrations. Samples may also be analyzed for ranibizumab.

#### ***Unscheduled collection of vitreous samples (optional)***

If elective vitrectomy surgery is medically necessary, a vitreous sample can be obtained from the study eye from patients who provide additional (optional) consent to participate in vitreous collection for the measurement of RO6867461 and biomarker concentrations.

Samples may also be analyzed for ranibizumab. A blood sample for PK measurement should be taken at the same time.

#### **EFFICACY OUTCOME MEASURES**

The primary efficacy outcome measure for this study is the mean change from baseline BCVA at Week 36 using the ETDRS-modified charts.

The secondary efficacy outcome measures for this study include BCVA and anatomical PD imaging measures relevant to the mechanism of action of RO6867461 as follows:

##### ***BCVA***

- Proportion of patients gaining  $\geq 15$  letters from baseline BCVA at Week 36
- Proportion of patients with BCVA of 20/40 or better at Week 36
- Proportion of patients with BCVA of 20/200 or worse at Week 36

##### ***Anatomic outcome measures using SD-OCT***

- Mean change from baseline in foveal center point thickness at Week 36
- Mean change from baseline in mean central subfield thickness (1 mm diameter) at Week 36
- Proportion of patients with no intraretinal fluid, subretinal fluid, cysts, or pigment epithelial detachment at Week 36

##### ***Anatomic outcome measures using FFA***

- Mean change from baseline in total area of CNV at Week 36
- Mean change from baseline in total area of CNV component at Week 36
- Mean change from baseline in total area of leakage at Week 36

#### **EXPLORATORY OUTCOME MEASURES**

The exploratory outcome measures for this study include but are not limited to the following:

- Biomarkers in plasma related to angiogenesis and inflammation
- Pro-angiogenic factors in aqueous humor and vitreous samples for patients who provide consent to participate

---

#### **BIOMARKER/GENOTYPING SAMPLE COLLECTION**

##### **Biomarkers Plasma Samples**

All patients who have been enrolled in the study will have mandatory PD and exploratory biomarker plasma samples taken at the time-points indicated in the SoA. The PD and exploratory plasma samples will be collected to investigate biomarkers in plasma related to angiogenesis and inflammation.

##### **Clinical Genotyping (CG) Samples**

A mandatory whole blood sample will be taken for DNA extraction from every subject. The DNA may be used to study genes related to AMD (e.g., AMRS2, HTRA1, CFH, C3, etc.) as well as related to angiogenesis (e.g., VEGFA, VEGFR2, angiopoietin-2, angiopoietin-1 receptor [Tie-2], etc.), and the effect on the PK/PD/efficacy/safety of RO6867461. Data arising from this sample will be subject to the same confidentiality as the rest of the study. This specimen will be destroyed no later than 2 years after the final closure of the clinical database.

---

#### **INVESTIGATIONAL MEDICINAL PRODUCT(S)**

IMPs will include the two study drugs as follows:

- **RO6867461:** Vials of sterile, colorless to brownish, preservative-free solution of RO6867461 (120 mg/mL), for IVT administration of either 1.5 or 6 mg dose every 4 or 8 weeks  
Placebo is provided as sterile, colorless to slightly brownish, preservative-free liquid, used only for dilution of RO6867461 drug product to the appropriate clinical dose.
- **Comparator—Ranibizumab:** Vials containing ranibizumab solution (10 mg/mL), for IVT administration of a 0.5 mg dose every 4 weeks.

The double-masked design is achieved through strict independence of the pharmacist (or designated personnel) and Investigators who are preparing and administering study

**RO6867461—F. Hoffmann-La Roche Ltd**  
Statistical Analysis Plan BP29647

---

treatment, from the assessing Investigators and remaining site personnel.

#### **NON-INVESTIGATIONAL MEDICINAL PRODUCTS**

- **Sham:** Sham IVT administration will be delivered to patients in Arm D at Weeks 16, 24, and 32 to maintain double-masking throughout the study period.

---

#### **PROCEDURES**

Detailed SoA and procedures are tabulated in Appendix 1 and Appendix 2 of the protocol.

##### ***Screening***

Treatment-naive patients with CNV secondary to AMD who are willing to participate in the study and have given informed consent will undergo a thorough screening examination within 4 weeks of study treatment administration. The screening procedures as outlined in the SoA will include review of inclusion and exclusion criteria, medical history, physical examination, assessment of vital signs and ECG, serum pregnancy test for female of childbearing potential, and safety laboratory parameters. Imaging criteria for eligibility will be confirmed by a Central Reading Center before enrolment.

##### ***Treatment period***

On Day 1, baseline assessments will be conducted on the eligible patients, according to the SoA. Patients will receive their first IVT administration of either RO6867461 or comparator therapy according to the randomization schedule and following established standard procedures. Patients will return to the eye clinic for study treatment administration (every 4 weeks) and assessments as outlined in the SoA. Patients will be administered the same study treatment throughout the study period, except for the patients randomized to Arms D and E:

- Patients in Arm D will receive sham administrations on Weeks 16, 24, and 32 to maintain the double-masking throughout the every 8 weeks (Q8W) regimen period.
- Patients in Arm E will initially receive 3 injections of ranibizumab followed by 6 injections of RO6867461.

A post-treatment administration check of study eye will be performed for each patient immediately after treatment administration, by testing finger count vision, or hand motion and light perception. On the day of dosing, IOP will be monitored at 30 minutes post-treatment administration in the study eye, and if IOP  $\geq$  30 mmHg, IOP should be reassessed at 1 hour post-treatment administration. If IOP continues to be elevated, treatment should be undertaken at the discretion of the Investigator.

##### ***Final period***

Patients will return for final visits with assessments as outlined in the SoA 4 weeks after the last study treatment administration.

---

#### **STATISTICAL METHODS**

##### **SAFETY ANALYSES**

All patients who receive at least one administration of the study treatment will be included in the safety analysis. The safety data, including adverse events, reasons for withdrawal from study, laboratory data, concomitant medications, vital signs, and physical examination results will be listed and summarized descriptively.

As appropriate, listings, summary tables, and graphs (subject plot and/or mean plots) will be provided for safety and tolerability assessments.

Anti-RO6867461 antibody results (positive/negative) will be listed.

General adverse events will be listed and summarized by body system and preferred term using MedDRA. Ophthalmologic adverse events will be listed and summarized.

For laboratory data subject listings will be presented with abnormalities flagged.

##### **PHARMACOKINETIC ANALYSES**

A nonlinear mixed effects modeling approach (with NONMEM software) will be used to analyze the concentration-time data of RO6867461. Population and individual primary PK parameters (i.e., clearance and volumes) will be estimated and the influence of various covariates (e.g., gender, body weight, etc.) on these parameters will be investigated. The

data collected in this study may be pooled with data collected in the previous Phase I study as appropriate to build a PK model. Secondary PK parameters such as area under the concentration-time curve (AUC) and maximum plasma concentration observed ( $C_{max}$ ) will be derived from the individual post-hoc predictions. The results of this analysis will be reported in a separate document from the clinical study report.

#### **PHARMACODYNAMIC ANALYSES**

Individual and mean PD data and parameters will be presented by listings and descriptive summary statistics including means, geometric means, medians, ranges, standard deviations, and coefficients of variation.

An empirical drug-disease model of longitudinal BCVA previously developed on the ranibizumab database will be used to analyze the effect of RO6867461 on BCVA using a meta-analysis approach by integrating data from this study and ranibizumab clinical data.

A similar modeling approach will be used to analyze the relationship between RO6867461 exposure and BCVA. The influence of various baseline covariates on model parameters will be investigated. The PK/PD or dose/PD relationship will be characterized. The results will be reported in a separate document from the clinical study report.

#### **SAMPLE SIZE JUSTIFICATION**

##### **Sample size and power for treatment-naive population evaluation**

The sample size is based on the primary efficacy outcome of BCVA mean change from baseline to Week 36. Each RO6867461 dose or dose regimen group (Arms B, C, and D) will be compared to the control group (Arm A).

The power calculation is based on 68 patients randomized to Arm A, and 45 randomized to each of Arms B, C, and D, with drop-out rate of 10%. Assuming a standard deviation of 13.5 letters, this sample size would provide approximately 80% power to detect a true difference of 5.9 letters at the one-sided  $\alpha$  level of 10%. The minimum detectable difference would be approximately 3.5 letters.

##### **Sample size and power for anti-VEGF–incomplete-responder population evaluation**

The sample size is based on the primary efficacy outcome of BCVA mean change from Week 12 to Week 36 in the subset of anti-VEGF–incomplete-responders, between Arm A and Arm E.

The power calculation is based on 68 patients randomized to both Arms A and E, with 65% meeting the criteria for inclusion in anti-VEGF–incomplete-responder subgroup and a drop-out rate of 10%. Assuming a standard deviation of 9.7 letters, this sample size would provide around 80% power to detect a true difference of 4.7 letters at the one-sided  $\alpha$  level of 10%. The minimum detectable difference would be approximately 2.7 letters.

#### **PRIMARY ENDPOINT ANALYSIS**

Evaluation in the treatment naive population: The primary efficacy variable is the mean BCVA change from baseline to Week 36. The primary efficacy analysis will be performed using a Mixed Model for Repeated Measurement (MMRM) model.

Evaluation in the anti-VEGF–incomplete-responder population: The primary efficacy variable is the mean BCVA change from Week 12 to Week 36. The primary efficacy analysis will be performed using a MMRM model.

---

---

**INTERIM ANALYSES**

An interim analysis may be conducted to allow for adapting the sample size.

An interim analysis of efficacy may be conducted for administrative reasons.

Up to two additional interim analyses may be conducted for efficacy.

---

**OTHER CONSIDERATIONS**

N/A

---

**LIST OF PROHIBITED MEDICATIONS*****Concomitant therapy***

Patients who use maintenance therapy other than those required to treat *wet AMD* (wAMD) should continue its use.

The decision to administer antimicrobial drops before and after the IVT administration is at the discretion of the Investigator.

***Excluded therapy***

At the discretion of the Investigator, patients may continue to receive all medications and standard treatments administered for other conditions except in the following instances:

- Concurrent use of systemic anti-VEGF agents
- Concurrent use of IVT anti-VEGF therapy in the fellow eye within 7 days before or after study eye treatment
- Concurrent use of IVT or subtenon corticosteroids in either eye, except as required to treat adverse events
- Concurrent use of photocoagulation or photodynamic therapy with verteporfin in the study eye for neovascular AMD

**Appendix 2  
Schedule of Assessments**

Week	Screening	Week 1		Week 4	Week 8	Week 12	Week 13	Week 16	Week 20	Week 24	Week 28	Week 32	Week 36 Final Visit	Early Termination Visit	Unscheduled
		Day 1	Day 7	Day 28	Day 56	Day 84	Day 91	Day 112	Day 140	Day 168	Day 196	Day 224	Day 252	Day +7	
Day	D-28 to D-1		+/-3	+/-3	+/-3	+/-3	-4/+3 m	+/-3	+/-3	+/-3	+/-3	+/-3	+/-3	+7	
Visit Window															
Assessments															
Informed Consent	X														
Eligibility	X	X a													
Demography	X														
Medical History	X	X													
Physical Examination	X												X	X	
Anthropometric Measurements	X												X	X	
Vital Signs a,b	X	2 k	X	2	2	2	X	2	2	2	2	2	X	X	X
ECG-12 lead	X												X	X	X
Hematology	X					X							X	X	X
Blood Chemistry	X					X							X	X	X
Urinalysis	X					X							X	X	X
Coagulation	X														X
Pregnancy Test	X														X

Week	Screening	Week 1		Week 4	Week 8	Week 12	Week 13	Week 16	Week 20	Week 24	Week 28	Week 32	Week 36 Final Visit	Early Termination Visit	Unscheduled
		Day 1	Day 7												
Day	D-28 to D-1			Day 28	Day 56	Day 84	Day 91	Day 112	Day 140	Day 168	Day 196	Day 224	Day 252		
Visit Window			+/-3	+/-3	+/-3	+/-3	-4/+3 m	+/-3	+/-3	+/-3	+/-3	+/-3	+/-3	+7	
Assessments															
Administration of Study Medication		X		X	X	X		X or sham	X	X or sham	X	X or sham			
Safety Finger Count Vision c,d		X		X	X	X		X	X	X	X	X			
IOP b,e	X	3 k,l	X	3 l	3 l	3 l	X	3 l	X	X	X				
BCVA a,e	X	X k		X	X	X		X	X	X	X	X	X	X	X
LLVA e		X				X							X	X	X
Slit Lamp a,e	X	X k	X	X	X	X	X	X	X	X	X	X	X	X	X
Ophthalmoscopy a	X	X k	X	X	X	X	X	X	X	X	X	X	X	X	X
Fundus Photography a	X	X k				X							X	X	X
Fundus Autofluorescence a	X					X							X	X	
SD-OCT a	X	X k	X	X	X	X	X	X	X	X	X	X	X	X	X
Fundus Fluorescein Angiography a	X					X							X	X	X
IndoCyanine Green Angiography a	X					X							X	X	X

Week	Screening	Week 1		Week 4	Week 8	Week 12	Week 13	Week 16	Week 20	Week 24	Week 28	Week 32	Week 36 Final Visit	Early Termination Visit	Unscheduled
		Day 1	Day 7	Day 28	Day 56	Day 84	Day 91	Day 112	Day 140	Day 168	Day 196	Day 224	Day 252		
Day	D-28 to D-1		+/-3	+/-3	+/-3	+/-3	-4/+3 m	+/-3	+/-3	+/-3	+/-3	+/-3	+/-3		
Visit Window														+7	
Assessments															
PK Sample a		X		X		X	X	X		X			X	X	X
PD Biomarkers Sample a		X		X		X	X	X		X			X	X	X
Exploratory Plasma Biomarker Sample a		X		X		X				X			X		
Aqueous Humor Sample (optional) a,d,i,g		X				X						X			X
Vitreous Humor + Blood Samples (optional) f,h												X			X
Clinical Genotyping Sample a,i,j		X													
Anti-Drug Antibody (ADA) a		X		X		X		X		X			X	X	X
Adverse Events a	X	X	X	X	X	X	X	X	X	X	X	X	X	X	X
Previous and Concomitant Treatments	X	X	X	X	X	X	X	X	X	X	X	X	X	X	X

- a Assessment prior to drug administration on days where study treatment is administered
- b Multiple assessments on a single visit day, details on timing on a separate table
- c Finger count vision assessment asap after, and within maximum of 15 min from study treatment administration
- d Assessment in study eye only
- e Performed prior to pupil dilation
- f Optional sample. Additional consent required from the patient
- g Unscheduled sample could be obtained at other or additional planned visits at the discretion of the Investigator in agreement with the participating patient
- h Only in case of vitrectomy surgery during the study and if vitreous sampling is feasible. A blood sample for plasma preparation should be drawn at the same time
- i Mandatory, except in countries where IRB/EC does not approve.
- j At Day 1 but can be done at any other visit if the sample not collected at baseline.
- k Baseline assessments
- l Assessment post-treatment administration in study eye only
- m Relative to the previous study treatment administration date (Week 12)

### Appendix 3 Definition of ATE

ATE events are non-fatal stroke, non-fatal myocardial infarction, or vascular death (including deaths of unknown cause). They are defined as the following MedDRA terms/baskets:

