#### Myocardial infarction

SMQ Broad | Myocardial infarction (SMQ)

PT | Coronary arterial stent insertion

PT | Coronary artery bypass

PT | Coronary endarterectomy

PT | Coronary revascularisation

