#### Non-myocardial arterial thromboembolic events (ATEs)

SMQ Narrow | Haemorrhagic cerebrovascular conditions

SMQ Narrow | Ischaemic cerebrovascular conditions

PT | Amaurosis

PT | Amaurosis fugax

PT | Aortic bypass

PT | Aortic embolus

PT | Aortic surgery

PT | Aortic thrombosis

PT | Aortogram abnormal

PT | Arterectomy

PT | Arterectomy with graft replacement

PT | Arterial bypass operation

PT | Arterial graft

PT | Arterial occlusive disease

PT | Arterial stent insertion

PT | Arterial therapeutic procedure

PT | Arterial thrombosis

PT | Arteriogram abnormal

PT | Arteriogram carotid abnormal

PT | Atherectomy

PT | Blindness transient

PT | Carotid angioplasty

PT | Cerebral hypoperfusion

PT | Coeliac artery occlusion

PT | Embolia cutis medicamentosa

PT | Embolism

PT | Embolism arterial

PT | Endarterectomy

PT | Femoral artery embolism

PT | Femoral artery occlusion

PT | Hepatic artery embolism

PT | Hepatic artery occlusion

PT | Hepatic artery thrombosis

PT | Hypothenar hammer syndrome

PT | Iliac artery embolism  
 PT | Iliac artery occlusion  
 PT | Intra-aortic balloon placement  
 PT | Intraoperative cerebral artery occlusion  
 PT | Leriche syndrome  
 PT | Mesenteric arteriosclerosis  
 PT | Mesenteric artery embolism  
 PT | Mesenteric artery stenosis  
 PT | Mesenteric artery stent insertion  
 PT | Mesenteric artery thrombosis  
 PT | Microembolism  
 PT | Penile artery occlusion  
 PT | Percutaneous coronary intervention  
 PT | Peripheral arterial occlusive disease  
 PT | Peripheral arterial reocclusion  
 PT | Peripheral artery angioplasty  
 PT | Peripheral artery bypass  
 PT | Peripheral artery stent insertion  
 PT | Peripheral artery thrombosis  
 PT | Peripheral embolism  
 PT | Peripheral endarterectomy  
 PT | Popliteal artery entrapment syndrome  
 PT | Pulmonary artery therapeutic procedure  
 PT | Pulmonary artery thrombosis  
 PT | Pulmonary endarterectomy  
 PT | Renal artery angioplasty  
 PT | Renal artery occlusion  
 PT | Renal artery thrombosis  
 PT | Renal embolism  
 PT | Splenic embolism  
 PT | Stress cardiomyopathy  
 PT | Subclavian artery embolism  
 PT | Subclavian artery occlusion  
 PT | Subclavian artery thrombosis  
 PT | Superior mesenteric artery syndrome  
 PT | Thromboembolectomy  
 PT | Thrombotic microangiopathy  
 PT | Thrombotic thrombocytopenic purpura  
 PT | Truncus coeliacus thrombosis  
 PT | Visual acuity reduced transiently

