#### Venous thromboembolism

PT | Axillary vein thrombosis  
 PT | Budd-Chiari syndrome  
 PT | Catheterisation venous  
 PT | Cavernous sinus thrombosis  
 PT | Central venous catheterisation  
 PT | Cerebral venous thrombosis  
 PT | Compression stockings application  
 PT | Deep vein thrombosis

PT | Deep vein thrombosis postoperative  
 PT | Embolism  
 PT | Embolism venous  
 PT | Hepatic vein occlusion  
 PT | Hepatic vein thrombosis  
 PT | Homans' sign positive  
 PT | Iliac vein occlusion  
 PT | Inferior vena cava syndrome  
 PT | Inferior vena caval occlusion  
 PT | Intracranial venous sinus thrombosis  
 PT | Intravenous catheter management  
 PT | Jugular vein thrombosis  
 PT | May-Thurner syndrome  
 PT | Mesenteric vein thrombosis  
 PT | Obstetrical pulmonary embolism  
 PT | Obstructive shock  
 PT | Ovarian vein thrombosis  
 PT | Paget-Schroetter syndrome  
 PT | Pelvic venous thrombosis  
 PT | Penile vein thrombosis  
 PT | Phlebectomy  
 PT | Phleboplasty  
 PT | Portal vein cavernous transformation  
 PT | Portal vein occlusion  
 PT | Portal vein thrombosis  
 PT | Post procedural pulmonary embolism  
 PT | Post thrombotic syndrome  
 PT | Postoperative thrombosis  
 PT | Postpartum venous thrombosis  
 PT | Pulmonary embolism  
 PT | Pulmonary infarction  
 PT | Pulmonary microemboli  
 PT | Pulmonary thrombosis  
 PT | Pulmonary vein occlusion  
 PT | Pulmonary veno-occlusive disease  
 PT | Pulmonary venous thrombosis  
 PT | Renal vein embolism  
 PT | Renal vein occlusion  
 PT | Renal vein thrombosis  
 PT | SI QIII TIII pattern  
 PT | Splenic vein occlusion  
 PT | Splenic vein thrombosis  
 PT | Subclavian vein thrombosis  
 PT | Superior sagittal sinus thrombosis  
 PT | Superior vena cava syndrome  
 PT | Thrombophlebitis  
 PT | Thrombophlebitis migrans  
 PT | Thrombophlebitis neonatal  
 PT | Thrombophlebitis superficial  
 PT | Thrombosed varicose vein  
 PT | Thrombosis corpora cavernosa

PT | Transverse sinus thrombosis  
PT | Vascular graft  
PT | Vena cava embolism  
PT | Vena cava filter insertion  
PT | Vena cava thrombosis  
PT | Venogram abnormal  
PT | Venocclusive disease  
PT | Venocclusive liver disease  
PT | Venous occlusion  
PT | Venous operation  
PT | Venous recanalisation  
PT | Venous stent insertion  
PT | Venous thrombosis  
PT | Venous thrombosis in pregnancy  
PT | Venous thrombosis limb  
PT | Venous thrombosis neonatal

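### The MedDRA lists in SAP Appendix 3 do not match its stated ATE definition, and no rule handles fatal outcome or unexplained death

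*SAP*

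**What the plan says.** SAP section 4.6.1 promises separate summaries of ATE events and refers to Appendix 3 for their definition. Appendix 3 opens with a three-part definition: "ATE events are non-fatal stroke, non-fatal myocardial infarction, or vascular death (including deaths of unknown cause"). The next sentence ties it to term lists: "They are defined as the following MedDRA terms/baskets".

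Three headed lists follow:

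- **Myocardial infarction:** one broad standardised MedDRA query (SMQ) and four preferred terms (PTs), all coronary procedures, for example "PT | Coronary artery bypass".
- **Arterial,** headed "Non-myocardial arterial thromboembolic events (ATEs"): two narrow cerebrovascular SMQs and a long PT list, with entries such as "PT | Renal artery thrombosis", "PT | Femoral artery embolism" and "PT | Percutaneous coronary intervention".
- **Venous,** headed "Venous thromboembolism": PTs only.

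On deaths, Protocol section 5.3.5.7 treats death as an outcome. The adverse event recorded is the condition that caused it. A death whose cause cannot be established is recorded as an unexplained death, and sudden death is reserved for abrupt, presumed cardiac deaths.

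**The concern.** The sentence and the lists are presented as the same definition, yet they select different events. A non-fatal femoral artery embolism is not an ATE by the sentence but is one by the list. A non-fatal deep vein thrombosis is venous and fits no part of the sentence, yet it sits under the same lead-in.

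The sentence also depends on whether an event was fatal, and nothing in Appendix 3 or section 4.6.1 uses that information. What is at stake is the one adverse event category that section 4.6.1 defines in its own appendix. If the choice between sentence and list is left open, it may be made after the arms are known.

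**Working it through.** The plan states no figure to reproduce. The check sets the definition against the lists and counts the printed rows of Appendix 3.

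**1. Size of the lists**

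| Basket | SMQs | Printed PTs |
|---|---|---|
| Myocardial infarction | 1 | 4 |
| Arterial, non-myocardial | 2 | 72 |
| Venous | 0 | 75 |
| Total | 3 | 4 + 72 + 75 = 151 |

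*Embolism* appears in both the arterial and the venous list, so 151 − 1 = 150 PTs are distinct. The venous list is 75 of 151 printed rows. That is not its share of the search, because the contents of the three SMQs that carry infarction and stroke are not given.

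**2. Arterial terms at other sites**

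Arterial rows naming a site other than heart, brain, carotid arteries or eye: peripheral 8, aortic 6, mesenteric 6, renal 4, hepatic 3, pulmonary 3, subclavian 3, coeliac 2, femoral 2, iliac 2, penile 1, popliteal 1, splenic 1.

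8 + 6 + 6 + 4 + 3 + 3 + 3 + 2 + 2 + 2 + 1 + 1 + 1 = 42, and 42 / 72 = 58.3%.

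Twelve of these are procedures or imaging findings: four aortic, one mesenteric, four peripheral, two pulmonary, one renal. That leaves 42 − 12 = 30 disease terms. Rows with no stated site, such as *Arterial thrombosis*, are not counted. The total moves slightly with the classification: adding Leriche and hypothenar hammer syndromes, whose names print no site, and dropping the intra-aortic balloon gives 42 + 2 − 1 = 43.

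**3. Placement of terms**

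Five coronary procedures are printed. Four are in the infarction basket; percutaneous coronary intervention is in the basket headed non-myocardial.

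**4. Fatal outcome**

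- By Protocol 5.3.5.7, a fatal infarction and a non-fatal one are recorded under the condition itself. A term search returns both together.
- The sentence needs them separated: the non-fatal event is one component, the fatal one belongs to vascular death. No rule does this.
- PTs whose names contain death, fatal, sudden or unexplained: 0 of 151. A death recorded as unexplained therefore has no stated route into the summary, although the sentence includes deaths of unknown cause.
- Sudden death is not a printed PT either. Whether the infarction SMQ retrieves it cannot be told from the documents. Even if an SMQ contains death terms, that supplies no rule for separating fatal from non-fatal events.

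**The case against.** The strongest reply is that little depends on this. ATE is not among the safety outcome measures in SAP 2.2.6, nor among the adverse events of special interest in Protocol 5.1.3. No test or decision rule uses an ATE count, the study is described as hypothesis-generating, and every event still appears in the adverse event and serious adverse event tables. All of that stands, and it limits the weight of the point.

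Second, the three lists carry separate headings, so they may be meant for separate tables. The List of Planned Outputs, which SAP 4.6 cites and which is not among the documents, may show this. If so, the venous basket is only mislabelled. That would not explain the arterial terms at other sites or supply a rule for fatal outcome.

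Third, the venous basket and the misplaced terms do not do full harm together. Venous events enter an ATE total only if baskets are pooled. The duplicate *Embolism* and the stray coronary term distort counts only if baskets are reported separately; in a pooled count of patients they change nothing. This is fair, and it shows why the SAP must say which applies.

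Fourth, the plan states that deaths of unknown cause count, and the protocol fixes the term under which they are recorded, so only a derivation line is missing. That is correct for unexplained deaths and makes the remedy easy. But Appendix 3 says the events are defined by the lists, and followed literally the lists leave those deaths out.

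**Conclusion.** The concern holds. Appendix 3 contains two definitions that disagree, and the one a programmer would implement gives a summary that differs from the stated definition. It admits non-fatal arterial events elsewhere in the body (30 disease terms and 12 procedure or imaging terms name such sites), admits venous events if baskets are pooled, does not separate fatal from non-fatal infarction and stroke, and gives no way to count unexplained deaths.

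The counts describe the printed list, not patients; the documents give no event rates from which to estimate the effect. The conclusion does not depend on what the SMQs contain. The venous point becomes a labelling error if the baskets are tabulated separately; the arterial and fatal-outcome points hold either way. The consequence is limited to a descriptive safety summary, so this should be corrected before unmasking but does not threaten the efficacy conclusions.

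**What to change.** Amend Appendix 3 before unmasking:

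1. Take the venous list out of the ATE definition and report it as a separately titled venous thromboembolism summary.
2. Add a rule that uses the recorded fatal outcome to separate vascular death from non-fatal infarction and stroke, says which causes of death count as vascular, brings in deaths recorded as unexplained, and states how sudden death is classified.
3. Make the sentence and the arterial list agree. Either limit the list to infarction and stroke, or keep the broad list as a separate category of arterial thromboembolic events and procedures with its own definition. Which procedure and transient visual terms stay in that category is for the sponsor to decide and record.
4. Assign *Embolism* to one basket, put all five coronary procedures in one basket, and state whether any baskets are pooled.

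The cost is an edit to one appendix and the matching programming. It uses adverse event terms and outcomes that are already collected.
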